9.3. Concomitant and Other Medications

Concomitant medications are coded using the World Health Organization (WHO) drug dictionary (1 Mar 2016 DDE+HD B2) for anatomical therapeutic chemical classification (ATC) and preferred drug name. A patient who used multiple medications are counted only once for each ATC and preferred drug name. ATC and preferred drug name within each ATC are sorted alphabetically. Coded concomitant medications are summarized by treatment analysis group (Section 4.5). Percentages are based on the number of patients in the safety analysis set.

A concomitant medication is any medication taken at the time of first study treatment during the RANGER study or a medication that was started after the start of RANGER study drug dosing. Specifically, concomitant medications are medications

- that are continued from CATALYST or LARIAT and continued after the first study drug dosing, or
- that have start dates or stop dates within the treatment period.

Concomitant medications are summarized for each treatment analysis group by WHO ATC class and preferred name. Patients may have more than one medication per ATC class and preferred name. At each level of patient summarization, a patient is counted once if he/she reported one or more medications at that level. Each summary is ordered by descending order of incidence of ATC class and preferred name within each ATC class.

Concomitant medications include those with an end date after the first study drug administration as well as medications without an end date. Medications with an end date on the date of first study drug administration are not be considered concomitant medications.

9.3.1. Missing and Partial Concomitant and Other Medication Start and Stop Dates

Missing and partial concomitant medication start and stop dates are detailed in Section 6.6.2.

9.4. Summaries of Laboratory Results

Laboratory data are summarized at baseline and at each time point by treatment analysis group (Section 4.5). Only values obtained within analysis study windows (Section 6.5.5) are included in by-visit summary statistics

Patients falling into the following four clinical meaningful categories are listed.

In addition, the number and percentage of patients in the following four clinical meaningful categories is summarized at each analysis visit by treatment analysis group (Section 4.5).

- BNP > 200 pg/mL
- BNP increase from baseline > 100%
- NT-proBNP > 1000 pg/mL
- NT-proBNP increase from baseline > 100%

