**Table 3: Schedule of Assessments**

Assessment \ Study Week (Day)	Day 1 a	Week 1 (Phone) Day 3±2	Week 1 Day 7±3	Week 2 (Phone) Day 10±2	Week 2 Day 14±3	Week 3 (Phone) Day 21±2	Week 4 Day 28±3	Week 4 (Phone) Day 31±2	Week 5 (Phone) Day 38±2	Week 6 Day 42±3	Week 8 Day 56±3	Week 24±3, Every 24 Weeks	End of Study Visit b
Informed consent	X												
Inclusion/Exclusion	X												
Prior and Concomitant medications	X c	X	X	X	X	X	X	X	X	X	X	X	X
Current PAH background medications	X c	X	X	X	X	X	X	X	X	X	X	X	X
Weight at home	X	X	X	X	X	X	X	X	X	X	X		
Weight in clinic	X c		X		X		X			X	X	X	X
Vital sign measurements	X c		X		X		X			X	X	X	X
Physical examination	X c		X		X		X			X	X	X	X
Pregnancy test d	X c											X	
Dispense study drug	X						X					X	
Collect study drug							X					X	X
Telephone contact		X		X		X		X	X				
Adverse event collection	X c	X	X	X	X	X	X	X	X	X	X	X	X
Clinical Chemistries f	X c		X		X		X			X	X	X	X
BNP and/or NT-Pro BNP	X c		X		X		X			X	X	X	X
6-min walk test	X c											X	X
Dyspnea and fatigue g	X c											X	X
WHO functional class	X c											X	X

a On Day 1, all procedures should be performed before study drug administration for patients who are treatment-compliant and have previously participated in clinical studies with bardoxolone methyl.

b After the Week 24 visit, patients will continue to be assessed in person every 24 weeks. The End of Study visit should occur within 30 days after the patient receives their final dose of study medication under this protocol. Patients who will be discontinued from the study prior to the completion of the study must also complete all End-of-Study assessments.

c Day 1 assessments should be performed as part of End-of-Treatment or Follow-up visit procedures from a prior study with bardoxolone methyl.

d A serum pregnancy test will be performed at any point in time if a pregnancy is suspected. All other pregnancy assessments will be urine pregnancy tests. Additional pregnancy assessments will be performed more frequently if required by local law or requested by local health authorities or IRBs/ECs.

e AE assessments on Day 1 should be performed following study drug administration.

f Clinical chemistries will be analyzed locally.

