#### **11.6. Recording Adverse Events**

All conditions present prior to the administration of the first dose of study drug (Day 1) in a previous study with bardoxolone methyl should be documented as medical history in a previous study with bardoxolone methyl. After the first dose, documentation of AEs shall continue until 30 days following administration of the final dose of study medication under this protocol (*i.e.*, through the End-of-Treatment visit), regardless of the relationship of the AE to study drug. Information to be collected will include type of event, date of onset, date of resolution, investigator-specified assessment of severity and relationship to study drug, seriousness, as well as any action taken.

While an AE is ongoing, changes in the severity (*e.g.*, worsening and improving) should be noted in the source documents, but when documenting the AE, only the total duration and greatest severity should be recorded in the eCRF. AEs characterized as intermittent will require documentation of onset and duration.

All drug-related (possibly, probably, or definitely related, see [Section 11.4](#)) AEs and abnormal laboratory test results reported or observed during the study must be followed to resolution (either return to baseline or within normal limits). All other AEs will be followed through the final visit indicated in [Table 3](#), as appropriate.

AEs resulting from concurrent illnesses, reactions to concurrent illnesses, reactions to concurrent medications, or progression of disease states must also be reported. Preexisting conditions (present before the start of the AE collection period) will be considered concurrent medical conditions and should NOT be recorded as AEs. However, if the patient experiences a worsening or complication of such a concurrent condition, the worsening or complication shall be recorded as an AE. Investigators shall ensure that the AE term recorded captures the change in the condition (*e.g.*, “worsening of...”). Any improvement in condition shall be documented per [Section 9.10.7](#).

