4.6. Clinical Assessments

All patients in RANGER follow the same visit and assessment schedule. RANGER Day 1 is defined as the first day treatment is dispensed to the patient for the RANGER, following completion of CATALYST or LARIAT. All other RANGER visits are relative to RANGER Day 1. Patients are scheduled for in-person assessments during treatment in the RANGER at Day 1, Week 1, Week 2, Week 4, Week 6, Week 8, Week 24, and every 24 weeks thereafter. Patients are also be assessed by telephone contact on Days 3, 10, 21, 31, and 38.

Table 2: RANGER Schedule of Assessments

Assessment \ Study Week (Day)	Day 1 ^a	Week 1 (Phone) Day 3±2	Week 1 Day 7±3	Week 2 (Phone) Day 10±2	Week 2 Day 14±3	Week 3 (Phone) Day 21±2	Week 4 Day 28±3	Week 4 (Phone) Day 31±2	Week 5 (Phone) Day 38±2	Week 6 Day 42±3	Week 8 Day 56±3	Week 24±3, Every 24 Weeks	End of Study Visit ^b
Informed consent	X												
Inclusion/Exclusion	X												
Prior and Concomitant medications	X ^c	X	X	X	X	X	X	X	X	X	X	X	X
Current background medications	X ^c	X	X	X	X	X	X	X	X	X	X	X	X
Weight at home	X	X	X	X	X	X	X	X	X	X	X		
Weight in clinic	X ^c		X		X		X			X	X	X	X
Vital sign measurements	X ^c		X		X		X			X	X	X	X
Physical examination	X ^c		X		X		X			X	X	X	X
Pregnancy test ^d	X ^c											X	
Dispense study drug	X						X					X	
Collect study drug							X					X	X
Telephone contact		X		X		X		X	X				
Adverse event collection	X ^e	X	X	X	X	X	X	X	X	X	X	X	X
Clinical Chemistries ^f	X ^c		X		X		X			X	X	X	X
BNP and/or NT-Pro BNP	X ^c		X		X		X			X	X	X	X
6-min walk test	X ^c											X	X
Dyspnea and fatigue ^g	X ^c											X	X
WHO functional class	X ^c											X	X

Abbreviations: BNP, B-type natriuretic peptide; NT-proBNP, N-terminal pro B-type natriuretic peptide; WHO, World Health Organization; AE, adverse event; 6MWT, 6-minute walk test

^a On Day 1, all procedures should be performed before study drug administration for patients who are treatment-compliant and have previously participated in clinical studies with bardoxolone methyl.

^b After the Week 24 visit, patients will continue to be assessed in person every 24 weeks until bardoxolone methyl becomes commercially available. The End-of- Study visit should occur within 30 days after bardoxolone methyl becomes available through commercial channels. Patients who will be discontinued from the study prior to commercial availability of bardoxolone methyl must also complete all End-of-Study assessments.

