6.5.5. Visit Windows

Because clinical visits may occur outside protocol-specified windows, instead of relying on visit labels in the clinical database, analysis visits and their windows are defined using derived study day (Section 6.5.3). Study day is calculated using the actual date for each scheduled and unscheduled assessment and compared to the target study day for each analysis visit. Data analysis and summaries are based on the collection date that is closest to the protocol scheduled target study day (Table 3).

Table 3: Analysis Visits

Analysis Visit	Label	Target Study Day	Analysis Window
0	Day 1	1	1
1	Week 1	7	$2 \leq \text{Study Day} \leq 10$
2	Week 2	14	$11 \leq \text{Study Day} \leq 21$
4	Week 4	28	$22 \leq \text{Study Day} \leq 35$
6	Week 6	42	$36 \leq \text{Study Day} \leq 49$
8	Week 8	56	$50 \leq \text{Study Day} \leq 70$
24	Week 24	168	$140 \leq \text{Study Day} \leq 196$
48	Week 48	336	$308 \leq \text{Study Day} \leq 364$
72	Week 72	504	$476 \leq \text{Study Day} \leq 532$
96	Week 96	672	$644 \leq \text{Study Day} \leq 700$
120, 144, etc.	Week 120, Week 144, Every 24 Weeks Thereafter	Analysis Visit x 7	$([\text{Analysis Visit} \times 7] - 28) \leq \text{Study Day} \leq ([\text{Analysis Visit} \times 7] + 28)$
FU	Follow-up	28 days after last dose	$14 \leq \text{Days after last dose} \leq 35$

The safety follow-up is based on days since last dose. If more than one assessment exists during the follow-up after last dose, the one closest to 28 days following the date of the last study drug administration is used for analysis and summary.

If a parameter is assessed or measured more than once within a visit window, the one that is closest to the protocol-scheduled time point (or target study day) is used for the purposes of data analysis and summary. If two assessments are equidistant from a target study day, the earlier assessment is used. If the visit used for analysis includes two assessments on the same day, the average of the two measurements will be used.

Records from visits not closest to the target study day, and therefore not used in analyses, are presented in by-subject data listings.

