6.6.4. Missing Treatment or Study End Date

The study was terminated on March 30, 2020. If the treatment end date or study end date are missing, the date will be imputed as March 30, 2020. If the treatment end date or study end date are missing and no reason for treatment or study discontinuation are included in the CRF, the reason for treatment or study discontinuation will be study termination.

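### An End-of-Study BNP, NT-proBNP, weight or vital-sign value taken within 13 days of last dose can fall in no analysis window and so enter no by-visit table

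*SAP*

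**What the plan says.** SAP 9.4 names four BNP/NT-proBNP categories (two absolute thresholds, two increases of more than 100% from baseline) and states that "the number and percentage of patients in the following four clinical meaningful categories is summarized at each analysis visit by treatment analysis group". It also provides a listing: "Patients falling into the following four clinical meaningful categories are listed". By-visit statistics in SAP 9.4 (laboratory) and SAP 9.5 (vital signs, including weight) use only values inside a SAP 6.5.5 window, and SAP 6.5.4 builds change from baseline on the same rule.

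SAP 6.5.5 places each value by its derived study day and does not use the visit label in the database. SAP Table 3 has rows for Day 1, Weeks 1, 2, 4, 6 and 8, Week 24 and every 24 weeks after that. One further row, Follow-up, is tied to last dose: its target is "28 days after last dose" and its window is 14 to 35 days. There is no End-of-Study row. On values that are not used, SAP 6.5.5 says: "Records from visits not closest to the target study day, and therefore not used in analyses, are presented in by-subject data listings".

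Protocol Table 3 marks BNP and/or NT-proBNP, clinic weight and vital signs at the End-of-Study visit, including for patients who stop early. Its footnote b reads: "The End of Study visit should occur within 30 days after the patient receives their final dose of study medication under this protocol". SAP Table 2 footnote b dates the visit differently; the "visit should occur within 30 days after bardoxolone methyl becomes available through commercial channels". Neither text sets a 14-day minimum after last dose.

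**The concern.** The protocol schedules a measurement that the SAP's windows need not accept. Change from baseline in BNP, NT-proBNP, vital signs and weight is part of the primary safety endpoint (Protocol 6.2, SAP 3.2.1). An analyst who follows the SAP exactly could leave a compliant value of one of these measures out of every by-visit table.

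End-of-Study visits need not line up with the 24-week cycle. SAP 6.6.4 records that "The study was terminated on March 30, 2020". A patient still on treatment then would have stopped at a study day set by enrolment date, and patients who stop early do so on any day. What is at stake is a summary with a denominator for the end of treatment. The data themselves are kept.

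**Working it through.** **Inputs.** Windows and the Follow-up range: SAP Table 3. End-of-Study timing: Protocol Table 3 footnote b, taken as a delay of 0 to 30 days after last dose. Day count: SAP 6.5.3.

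**Step 1: reproduce the windows.** The rule printed for Week 120 onward is (week × 7) ± 28.
- Week 24: 168 ± 28 = 140-196
- Week 48: 336 ± 28 = 308-364
- Week 72: 504 ± 28 = 476-532
- Week 96: 672 ± 28 = 644-700

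All four match the printed windows.

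**Step 2: find the gaps.** The early windows run without a break through day 70. The uncovered days are 71-139 (69 days), 197-307 (111 days), 365-475 (111 days), and so on. After Week 24, each 168-day cycle has 111 uncovered days: 111/168 = 66.1%.

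**Step 3: compare the permitted delays with Follow-up.** Of the 31 delays 0-30, delays 14-30 (17) are inside Follow-up and delays 0-13 (14) come before it. SAP 6.5.3 adds 1 to days since last dose, a convention stated for listings. If it also governs the window, the delays before Follow-up are 0-12 (13 of 31).

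**Step 4: one case.** Last dose on day 245, End-of-Study visit 7 days later, so study day 252. Week 24 ended on day 196, Week 48 starts on day 308, and 7 is less than 14. The value is in no row.

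**Step 5: share in no window among visits made before Follow-up opens.** Assumption: last-dose day uniform over 1 to L, every pair of last-dose day and delay counted once. A value is missed if its study day is in a gap.

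| Last-dose days | Delay 0-13 | Delay 0-12 (with +1) |
|---|---|---|
| 1-56 | 0 (56 + 13 = 69, still covered) | 0 |
| 1-70 | 91/(70 × 14) = 0.093 | 78/(70 × 13) = 0.086 |
| 1-364 | 2611/(364 × 14) = 0.512 | 2418/(364 × 13) = 0.511 |
| 1-700 | 5719/(700 × 14) = 0.584 | 5304/(700 × 13) = 0.583 |
| 1-1000 | 8736/(1000 × 14) = 0.624 | 8112/(1000 × 13) = 0.624 |
| 700-867 (one late cycle) | 1554/(168 × 14) = 0.661 | 1443/(168 × 13) = 0.661 |

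**Step 6: share among all End-of-Study visits.** This is p × g, where p is the share of visits made before Follow-up opens and g is the figure from Step 5. The documents do not give p.
- p = 0: 0%
- p = 0.10: 0.10 × 0.512 = 5% to 0.10 × 0.661 = 7%
- p = 14/31 = 0.452 (delay uniform over 0-30): 0.452 × 0.512 = 23% to 0.452 × 0.661 = 30%; with the +1 count, p = 13/31 = 0.419, giving 21% to 28%
- p = 1: 51% to 66%

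**The case against.** The protocol has no separate follow-up visit, so the SAP's Follow-up row is most naturally the place meant for the End-of-Study visit. Protocol 11.6 supports this. It keeps adverse-event documentation open "until 30 days following administration of the final dose of study medication under this protocol" and ties the end of that period to the final visit. If sites work to day 30, every value lands in Follow-up. This stands as a reason to expect a small effect. It does not close the gap: 11.6 governs adverse-event recording, while footnote b, which sets the visit date, has no minimum.

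The consequence is also limited. All analyses are descriptive, out-of-window results are listed, patients in the four categories are listed, and adverse events are still tabulated. That stands too. The four categories are supplementary displays. The link to the primary safety endpoint runs through change from baseline.

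A reader might infer three stronger things that the documents do not support:
- **That a fifth to nearly a third of End-of-Study values are lost.** The 21-30% range needs delays spread evenly over 0-30 days, and nothing in either document says so.
- **That an in-window End-of-Study value passed over for a routine value nearer the target is also lost.** The patient already has a value in that row under a prespecified rule.
- **That the summaries are biased.** Nothing shows that the omitted values are higher or lower than those tabulated.

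**Conclusion.** The point holds as a minor inconsistency between the windows and the visit schedule. A compliant End-of-Study value taken 0-13 days after last dose (0-12 with the +1 count), on a study day in a gap, enters no by-visit table under SAP 9.4 or 9.5.

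The number of patients affected is unknown, because the documents give neither last-dose days nor End-of-Study delays. It is zero if all visits fall on days 14-30 or all last doses fall by day 56. Among visits made on days 0-13 it is about 51-66%, on the assumption that last-dose days are uniform over about a year or more.

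The zero for days 14-30 also needs true last-dose dates. SAP 6.6.4 imputes a missing treatment end date as 30 March 2020, and SAP 9.2 uses the last kit date for patients still on treatment at a data cut. Either can move a value out of Follow-up or make its delay negative.

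**What to change.** **Main change.** In SAP Table 3, add an End-of-Study row (or widen and relabel Follow-up) for BNP, NT-proBNP, weight and vital signs.
- Fill it from the visit recorded as End of Study, whatever its study day and with no condition on days since last dose. Imputed or kit-based end dates then cannot exclude a value.
- Report change from baseline and the four SAP 9.4 categories in that row.
- Show days since last dose, flag imputed end dates, and state that the row is not a last on-treatment value.
- Reconcile SAP Table 2 footnote b with Protocol Table 3 footnote b on the event from which the visit is dated.

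**Optional supplement.** In SAP 9.4, add the number and percentage of patients meeting each category at any post-baseline time through 35 days after last dose, the end of the Follow-up window, with unscheduled and End-of-Study values included. Because sampling is BNP and/or NT-proBNP, use assay-specific denominators: patients with at least one post-baseline value of that assay, and also a baseline value for the two categories based on increase. Show separately the patients not above the absolute threshold at baseline, and give exposure by group.

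**Cost.** SAP wording and a few table rows from scheduled data. The End-of-Study row pools values at different times off drug. Any-time percentages rise with follow-up and must be read beside exposure.

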9.5. Vital Signs

Vital signs assessments include systolic blood pressure (SBP, mmHg) and diastolic blood pressure (DBP, mmHg), body temperature (°C), heart rate (HR, bpm), weight (kg), and BMI (kg/m²). Only values obtained within analysis study windows (Section 6.5.5) are included in by-visit summary statistics. Vital signs are summarized at baseline and at each time point along with the change from baseline by treatment analysis group (Section 4.5). All data are listed.

Line plots of change from baseline of vital signs by visit and treatment analysis group (including overall patients) are generated up to and including study Week 120. In addition, line plots are generated by: CTD; non-CTD.

Vital signs are summarized by: CTD; non-CTD.

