### **9.10.6. Vital Sign Measurements**

Vital sign measurements include the patient's heart rate (beats/minute taken for at least 15 seconds), respiration rate, and body temperature. Blood pressure should be taken after the patient has rested in a sitting position for at least 5 minutes. The same arm (usually the non-

dominant arm) and the appropriate size cuff should be used for each measurement. Vital sign measurements should be taken as indicated in [Table 3](#).

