#### **9.10.7. Physical Examination**

A comprehensive physical examination must be performed by a physician, physician assistant, or registered nurse practitioner as indicated in [Table 3](#) and as documented within the table footnotes. The examination must include the following organ or body system assessments: head, eyes, ears, nose, throat, musculoskeletal, cardiovascular, lymphatic, respiratory, abdomen, skin, extremities, and neurological. Assessments of any specific signs or symptoms reported by the patient must also be performed and documented along with any other findings of note. Clinically significant findings at Day 1 must be recorded as medical history. Following the examination on Day 1, new or changed physical examination findings meeting the criteria for an adverse event must be recorded as an adverse event. If possible, the same individual should perform each physical examination on a patient during the study.

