### **12.2. Study Variables**

#### **12.2.1. Safety Variables**

The safety variables will include results of physical examinations, laboratory test results (BNP and NT-Pro BNP), vital sign measurements, weight, AEs, and SAEs.

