3.2. Study Endpoints

3.2.1. Primary Safety Endpoints:

Frequency, intensity, and relationship to study drug of adverse events (AEs) and serious adverse events (SAEs) and change from baseline in the following assessments: physical examinations, vital sign measurements, BNP, N-terminal pro-brain natriuretic peptide (NT-proBNP), and weight.

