9. SAFETY AND TOLERABILITY

Safety data (including AEs, vital signs, BNP, and NT-proBNP) are listed and summarized for patients in the safety population (Section 6.3.2) by treatment analysis group (Section 4.5).

The analysis visit windows (Section 6.5.5) are used for all safety analyses. Any results not included in summaries based on analysis visit window definitions are presented in data listings.

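### SAP 9.5 omits respiration rate from the vital signs it summarises, leaving that part of the primary safety endpoint incomplete; physical examination has no stated output of its own

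*SAP*

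**What the plan says.** Protocol 6.2 and SAP 3.2.1 define the primary safety endpoint in the same terms. Besides adverse events (AEs) and serious AEs, it covers "change from baseline in the following assessments: physical examinations, vital sign measurements, BNP, N-terminal pro-brain natriuretic peptide (NT-proBNP), and weight". The protocol's statistics section (12.2.1) agrees: "The safety variables will include results of physical examinations, laboratory test results (BNP and NT-Pro BNP), vital sign measurements, weight, AEs, and SAEs".

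Protocol 9.10.6 says what a vital sign is: "Vital sign measurements include the patient's heart rate (beats/minute taken for at least 15 seconds), respiration rate, and body temperature", with seated blood pressure added in the next sentence. Protocol Table 3 and SAP Table 2 mark vital signs and physical examination at Day 1, Weeks 1, 2, 4, 6, 8 and 24, every 24 weeks after that, and End of Study.

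SAP 9.5 gives the parameters for analysis: "Vital signs assessments include systolic blood pressure (SBP, mmHg) and diastolic blood pressure (DBP, mmHg), body temperature (°C), heart rate (HR, bpm), weight (kg"), followed by BMI. These are summarised at baseline and by visit with change from baseline, by treatment analysis group and by CTD status, with line plots to Week 120. The section also promises a listing of all the data.

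SAP 9 describes its scope as follows: "Safety data (including AEs, vital signs, BNP, and NT-proBNP) are listed and summarized". Physical examination is not named there or in 9.1 to 9.6. SAP 11 declares one departure from the protocol, the Week 1 visit. SAP 2 says that the SAP prevails where the two documents differ on planned analyses.

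**The concern.** SAP 9.5 is a specific list, with units, from which a programmer would build the vital-sign tables. A parameter that the protocol requires, and that belongs to the endpoint, is missing from it. Because the SAP prevails over the protocol, protocol 9.10.6 does not restore it. Because SAP 11 is silent, a reader cannot tell whether the omission was intended.

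Describing safety is the whole analytic purpose of this single-arm study, so the planned tables are its main product. If the SAP is followed literally, the study report will state an endpoint that its tables do not fully deliver. Under SAP 2, any analysis added after database lock counts as ad hoc. Physical examination raises a similar question: the endpoint promises change from baseline, and no section says how that will be shown.

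**Working it through.** No arithmetic beyond counting applies, and the plan gives no figure to reproduce. The check matches each measured quantity and each endpoint component to a planned output.

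**Step 1. Vital signs: protocol 9.10.6 against SAP 9.5.** Systolic and diastolic pressure are counted separately.

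| Quantity in protocol 9.10.6 | Change-from-baseline summary in SAP 9.5 |
|---|---|
| Systolic blood pressure | Yes |
| Diastolic blood pressure | Yes |
| Heart rate | Yes |
| Body temperature | Yes |
| Respiration rate | Not named |

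Four of five are covered, so 5 − 4 = 1 is not. The SAP list has six entries because it adds weight and BMI, which the protocol handles separately in 9.10.5.

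**Step 2. Endpoint components in SAP 3.2.1 against SAP 9.**

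| Component | Planned output |
|---|---|
| AEs and serious AEs | SAP 9.1 tables and listings |
| BNP, NT-proBNP | SAP 9.4 by-visit summaries and counts of increases above 100% |
| Weight | SAP 9.5 |
| Vital signs | SAP 9.5, without respiration rate |
| Physical examination | None of its own |

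Five assessments are named for change from baseline: physical examination, vital signs, BNP, NT-proBNP and weight. One of them (vital signs) is incomplete, and one (physical examination) has no dedicated output.

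**Step 3. How often the data are collected.** After Day 1 there are six clinic visits to Week 24 (Weeks 1, 2, 4, 6, 8, 24). With Day 1 that makes 6 + 1 = 7 scheduled readings per patient, then one every 24 weeks and one at End of Study. Enrolment is capped at 366 (SAP 4.3).

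**Step 4. Other routes into the report.**

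- *Respiration rate.* The full listing promised in SAP 9.5 may include it. A listing is not a change-from-baseline summary.
- *Physical examination.* Protocol 9.10.7 sends new or changed findings that qualify as AEs to the AE record, so they reach the treatment-emergent tables. The route is partial. Under protocol 11.6, signs that accompany a recorded diagnosis are not entered as separate AEs, and improvement in a condition is not recorded as an AE. The general listing rule in SAP 6 covers data behind tables and figures, and no examination table is planned.
- *Day 1 examination.* Protocol 9.10.7 says: "Clinically significant findings at Day 1 must be recorded as medical history". SAP 7.5 takes medical history from the parent-study Screening visit, so no planned summary displays the RANGER Day 1 findings.

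**The case against.** The case for leaving the plan alone has real weight.

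*The list in SAP 9.5 may not be exhaustive, and all data are to be listed.* This stands in part. A reader might infer that respiration rate is never reported. The documents do not support that, because it may well appear in the listing. What is missing is the summary. The list is unit-by-unit and carries no sign that its entries are only examples, so a programmer would not be expected to add to it.

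*Respiration rate is not itself an endpoint component.* This stands. A reader might infer that two components go unanalysed. In fact the vital-sign component is summarised for its other four quantities and is incomplete, not absent.

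*Examination findings already reach the AE tables.* This largely stands, within the limits in step 4. For physical examination the gap is mainly one of wording and listing.

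*Parent-study medical history does no harm.* This stands. A reader might infer that new findings would be misclassified. Treatment-emergent status depends on onset relative to the first RANGER dose (SAP 6.6.3 and 9.1), not on the medical history table. Protocol 11.6 also places conditions that predate the first dose of the previous study in that study's medical history. Only the display of Day 1 findings is affected.

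*The clinical stake is not documented.* This stands. It is tempting to say that a fluid-overload or lung signal would be lost. Protocol 9.1.1 monitors fluid status through weight, laboratory data, natriuretic peptides, symptoms and edema and does not mention respiration rate. The documents give no figure for what respiration rate would add.

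**Conclusion.** The point holds for respiration rate. A scheduled vital sign that falls within the primary safety endpoint has no planned change-from-baseline summary, and the departure is undeclared. Its size is one of five vital-sign quantities. Physical examination is secondary: the SAP needs to say how the component is reported.

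The documents do not show a wrong result, a lost safety signal or a misclassified event. The study has no comparator and was terminated on March 30, 2020, and all analyses are descriptive. No error rate, sample size or decision rule is affected.

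Two assumptions apply. First, respiration rate was entered in the study database as protocol 9.10.6 implies; the eCRF is not among the documents. Second, 9.10.6 reads the same in Protocol Version 3.0, on which the SAP is based. The protocol reviewed differs from the SAP on treatment duration, but the two schedules mark vital signs at the same visits, and the SAP's amendment table reports no change to how vital signs are defined.

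**What to change.** 1. Add respiration rate (breaths/min) to the SAP 9.5 parameter list so that it enters the by-visit and change-from-baseline tables. The cost is one line of SAP text and one more parameter in an existing program. If respiration rate was left out on purpose, say so in SAP 11 with the reason.
2. For physical examination, choose one of two routes. Either add a by-patient listing of examination findings against RANGER Day 1, where they are captured, or state in SAP 11 that this component is reported only through AEs. The second route costs a sentence. The first depends on what the eCRF holds, since the documents show only medical history and AE entries as places where findings are recorded.

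Both changes belong before database lock. If the lock has passed, report the respiration-rate table as an identified addition, as SAP 2 requires. Extra line plots or subgroup splits for respiration rate are optional.
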